5.5.2. Part B

The dose level of GSK3358699 selected to be administered with or without a high fat meal in Part B will have been previously investigated in Part A of the study and will have demonstrated adequate exposure, safety and tolerability to support its inclusion in the food effect investigation. The dose of GSK3358699 administered will be decided by the dose escalation committee.

5.5.3. Part C

Five dosing cohorts are planned for Part C. Once-daily dosing (QD) of GSK3358699 is planned for 14 consecutive days in Cohorts 4 - 7 and for up to 14 consecutive days in Cohort 8. The selection of appropriate doses will be performed upon consideration of

available safety and tolerability, PK and PD data from Part A and/or any preceding repeat dose cohorts in Part C.

The dose of GM-CSF to be administered to participants in Part C will be 60 μ g/m². The dose of LPS to be administered to participants in Part C will be 0.75 ng/kg.

Administration of the challenge agents will be on Day 14 in Cohort 4 and is planned to be on the final day of dosing in Cohort 8; the time point will be based on an estimate of the intracellular acid kinetics determined in the preceeding cohorts of the study and will be no more than 24 h after dosing with GSK3358699 or placebo on that day.

Based on emerging data, the DEC may decide to modify the dosing frequency to less than once daily or more than once daily, as well as make other modifications as detailed in Section 7.2.

5.5.4. Human PK and PK/PD predictions

The PK of GSK3358699 in humans has been predicted by PBPK modelling using software Gastroplus. The human PBPK model was based on scaling of the monkey parameters, hepatic and renal clearance, except for the human acid metabolite (GSK3206944) liver clearance which was based on scaling of the dog *in vivo* liver clearance. Based on this model a compartment model was built for selecting doses and predicting exposures (see Section 5.5.1).

[figure not shown]
LPS-induced MCP-1 inhibition is considered a robust measurement of BET protein target engagement. Human predicted MCP-1 inhibition levels (Figure 5) were based on results from *in vitro* human whole blood assay (LPS stimulated) data which provided an estimated pIC₅₀ of 8.13, which translates to a plasma IC₅₀ of 4.8 ng/ml and a plasma IC₉₀ of 22.9 ng/ml (Hill slope=1.4).

As shown in Figure 4, Figure 5 and Table 2, the doses of GSK3358699 to be explored as part of the FTIH study have been carefully modelled to ensure a controlled dose escalation, such that the Brd4 BD1 IC₅₀ (25 ng/ml) is only exceeded at small multiples and only at the highest doses proposed. Brd4 BD1 is one of the two bromodomains present in the Brd4 protein and is used here as a comparative indicator of systemic bromodomain inhibition. Non-targeted bromodomain inhibitors have classically relied on sustained systemic concentrations over and above the Brd4 BD1 IC₉₀ to drive anti-inflammatory and anti-proliferative effects. Given the targeted nature of GSK3358699 and in contrast to prior clinical investigations with panBET inhibitors, GSK3358699 Brd4 BD1 IC₉₀ (128 ng/ml) will not be exceeded systemically at any dose planned.

[figure not shown]
Importantly, the potency advantage derived from the ESM ensures that even at these comparatively low levels of systemic BET inhibition, MCP-1 inhibition is expected to be essentially complete at doses greater than 20 mg GSK3358699 QD (Figure 5 and Table 2). Based on this modelling, the current anticipated GSK3358699 dose levels are considered appropriate to the objectives of this FTIH investigation.

Figure 4

GSK3358699 Predicted Human PK Profile

6. STUDY POPULATION

Prospective approval of protocol deviations to recruitment and enrollment criteria, also known as protocol waivers or exemptions, is not permitted.

6.1. Inclusion Criteria

Participants are eligible to be included in the study only if all of the following criteria apply:

Age

- 1. Participant age range:
 - a. Part A (Cohort 1 and 2, no LPS or GM-CSF administration, ie if choosing not to take part in Treatment Period 4); participants enrolled into the study must be 18 to 65 years of age inclusive at the time of signing the informed consent form.
 - b. Part A (Cohort 1 and 2, LPS or GM-CSF administration); participants enrolled into the study, must be 18 to 55 years of age inclusive, at the time of signing the informed consent.

- c. Part B (Cohort 3, no LPS or GM-CSF administration); participants enrolled into the study must be 18 to 65 years of age inclusive, at the time of signing the informed consent.
- d. Part C (Cohorts 5 to 7, no LPS or GM-CSF administration); participants enrolled into the study must be 18 to 65 years of age inclusive at the time of signing the informed consent form.
- e. Part C (Cohort 8, LPS or GM-CSF administration) Participants enrolled into the study must be 18 to 55 years of age inclusive at the time of signing the informed consent form.

Type of Participant and Disease Characteristics

2. Participants who are overtly healthy as determined by medical evaluation including medical history, physical examination, laboratory tests, and cardiac monitoring.

Weight

3. Body weight \geq 50 kg and body mass index (BMI) within the range 18.5-35.0 kg/m² (inclusive).

Sex

4. Male

a. Male participants:

Where relevant (see Section 12.5) male participants must agree to use contraception as detailed in Section 12.5 during the treatment Period and for at least 91 days, after the last dose of study treatment and refrain from donating sperm during this Period.

Informed Consent

5. Capable of giving signed informed consent as described in Appendix 3 which includes compliance with the requirements and restrictions listed in the informed consent form (ICF).

6.2. Exclusion Criteria

Participants are excluded from the study if any of the following criteria apply:

Medical Conditions

- 1. Current or chronic history of:
 - pancreatitis.
 - diabetes mellitus or impaired glucose tolerance.
 - gastrointestinal disease.
 - liver disease, or known hepatic or biliary abnormalities (with the exception of Gilbert's syndrome or asymptomatic gallstones).

- anaphylaxis, and /or anaphylactoid (resembling anaphylaxis) reactions [Sampson et al 2006].
- renal disease where clinically significant (minor abnormalities may be permitted base on discussion between investigator and medical monitor).
- respiratory disease or conditions including but not limited to asthma, chronic obstructive pulmonary disease (COPD), and bronchiectasis and any current respiratory infection (childhood asthma is not an exclusion criterion).
- sensitivity or severe allergic responses to any of the challenge agents or cantharidin, or components thereof or a history of drug or other allergy that, in the opinion of the Investigator or GSK Medical Monitor, contraindicates their participation.
- frequent vasovagal syncope.
- surgery requiring general anaesthetic or significant trauma in 3 months leading to study enrolment.
- relevant skin conditions (e.g. recent history of eczema or recurrent eczema, keloid, skin allergies, psoriasis, atopic dermatitis, and vitiligo) which in the opinion of the investigator could pose safety issues or cause interference with study procedures.
- sepsis.
- coagulation disorders.
- peripheral oedema, lymphangitis, lymphoedema, pleural or pericardial effusion.
- haemorrhage (eg sub-arachnoid) or hemophilia or a related bleeding disorder.
- 2. History of malignancies e.g. recurrent basal cell carcinoma, haematological malignancy.
- 3. For participants receiving cantharadin: Presence on either forearm of tattoos, naevi, hypertrophic scars, keloids, hyper– or hypo- pigmentation that may, in the opinion of the Investigator, interfere with study assessments. Participants with excessive hair or any skin abnormalities that may, in the opinion of the Investigator, interfere with study assessments.
- 4. History of cardiac disease e.g. congenital heart disease, valvular heart disease, ischemic heart disease, clinically significant atrial or ventricular arrhythmias, QTc prolongation, or cardiac arrest.
- 5. Family history of premature cardiovascular disease, long QT syndrome or sudden death.
- 6. QTcF > 450 msec, based on averaged QTcF values of triplicate ECGs obtained over a brief recording Period.

NOTES:

• The QTcF is the QT interval corrected for heart rate according to Fridericia's formula (QTcF) machine-read or manually over-read.

- For purposes of data analysis QTcF will be used as specified in the Reporting and Analysis Plan (RAP).
- 7. Any clinically relevant abnormality on the screening ECG.
- 8. Non-sustained ventricular tachycardia (NSVT) defined as ventricular triplet or longer), or more than 30 Ventricular Premature Depolarisation (VPD)/hour on screening Holter.
- 9. Has any condition that, in the opinion of the investigator, would make participation not be in the best interest (eg, compromise the well-being) of the subject or that could prevent, limit, or confound the protocol-specified assessments.

Prior/Concomitant Therapy

10. Unable or unwilling to refrain from taking prescription or non-prescription drugs (including vitamins and dietary or herbal supplements) within 7 days (or 14 days if the drug is a potential enzyme inducer) or 5 half-lives (whichever is longer) before the start of study treatment until completion of the follow-up visit. Paracetamol, at doses of ≤ 2 grams/day, is permitted for use any time during the study except as detailed in Section 7.7. Other concomitant medication may be considered on a case-by-case basis by the investigator in consultation with the Medical Monitor.

Prior/Concurrent Clinical Study Experience

- 11. The participant has participated in a clinical trial and has received an investigational product within the following time period prior to the first dosing day in the current study: 30 days, 5 half-lives or twice the duration of the biological effect of the investigational product (whichever is longer) or currently in a study of an investigational device.
- 12. Exposure to more than four new chemical entities within 12 months prior to the first dosing day.
- 13. Previous exposure to intravenous LPS in a clinical research setting.

Diagnostic assessments at screening

- 14. Alanine transaminase (ALT) >1.5x upper limit of normal (ULN).
- 15. Bilirubin >1.5xULN (isolated bilirubin >1.5xULN is acceptable if bilirubin is fractionated and direct bilirubin <35%).
- 16. Presence of hepatitis B surface antigen (HBsAg), positive hepatitis C antibody test result at screening or within 3 months prior to first dose of study treatment.
- 17. A positive pre-study drug/alcohol screen.
- 18. A positive test for human immunodeficiency virus (HIV) antibody.
- 19. Persistent clinically significant abnormal CRP levels at screening.
- 20. Persistent clinically significant abnormal white cell count (WCC) levels at screening (if clinically significant abnormality is detected, WCC can be retested as clinically indicated).

- 21. Platelets $< 150 \times 10^9$ /L.
- 22. Fasted Triglycerides >3.4 mmol/L.
- 23. Fasted Total cholesterol >7.7 mmol/L.
- 24. Fasted glucose \geq 7.0 mmol/L
- 25. Urinary cotinine levels indicative of smoking or history or regular use of tobacco- or nicotine-containing products within 3 months prior to screening.

Other Exclusions

- 26. History of regular alcohol consumption within 6 months of the study defined as:
 - an average weekly intake of >14 units. One unit is equivalent to 8 g of alcohol: a half-pint (~240 ml) of beer, 1 glass (125 ml) of wine or 1 (25 ml) measure of spirits.
- 27. Where participation in the study would result in donation of blood or blood products in excess of 500 mL within a 56 day period.
- 28. Unable to comply with precautions to minimise phototoxicity risk.

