2.3. Part C General Schedule of Activities Cohorts 5-7 (no challenges)

	Screening (up to 35 prior to Day 1)	Treatment Period																	Follow-up post-la	Notes
Procedure	up to 35 Days Day 1)	Day -1	Day 1	Day 2	Day 3	Day 4	Day 5	Day 6	Day 7	Day 8	Day 9	Day 10	Day 11	Day 12	Day 13	Day 14	Day 15	Day 16	Follow-up 1 (7-14 days post-last dose)	
General																				
Informed consent	Х																			
Inclusion and exclusion criteria	х	х																		Day -1 assessment is to recheck eligibility against medical conditions, prior therapy etc, but not against Day -1 clinical chemistry and haematology results (see Section 9.4.7).
Demography	Х	ļ	ļ	į	į	į	ļ	į	ļ	ļ	į	į	į	İ	İ	į	ļ	į		
Medical/medication/ drug/alcohol history	х	х																		Includes substance usage and family history of premature CV disease and current medical conditions.
Admission to unit for in-patient stay		Х																		
Discharge from Unit following in- patient stay																		x		
Outpatient visit	Х	1									1					1			Х	
Safety Assessments including	ety Assessments including laboratory tests																			
Full Physical Exam	Х																			
Brief Physical Exam		X			Ì			Ì				Ì	Ì			İ		X	Х	
Vital Signs	х	х	x	x		x				х				x	x	x	x	x	х	BP, HR, temperature, respiratory rate. See Section 2.3.1 for time points on Day 13, 14, 15 and 16. Measurements will be performed pre-dose on other dosing days.
12-Lead ECGs	x	x	x	x	x	x	x	x	x	x	x	x	x	x	x	x	x	x	x	12 Lead ECGs will be performed in triplicate at screening, Day-1, pre-dose Day 1, Day 4, Day 8, Day 14 and Day 16. Single ECGs will be performed at other time points and if any cardiac symptoms are experienced. ECGs to be performed prior to any blood draws or dosing scheduled for the same nominal time point.

	Screening (up to 35 prior to Day 1)							٦	reat	ment	Perio	bd							Follow-up post-la	Notes
Procedure	up to 35 Days Day 1)	Day -1	Day 1	Day 2	Day 3	Day 4	Day 5	Day 6	Day 7	Day 8	Day 9	Day 10	Day 11	Day 12	Day 13	Day 14	Day 15	Day 16	Follow-up 1 (7-14 days post-last dose)	
Telemetry			x			x				x						x				Continuous cardiac telemetry on each designated day from 1hr pre-dose until 24 h post-dose, and on other days if QTcF >450msec.
Holter monitoring (24 hours)	Х																			If a participant is rescreened the Holter will not need to be repeated.
HIV, Hep B, Hep C	Х	1	İ	İ	İ	1	İ	İ	Ì	Ì	1	1			1	1	İ	İ		

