Non-sustained ventricular tachycardia (NSVT)	• Four cases of asymptomatic, non-serious, non-severe and self-limiting NSVT were observed in this study (207546); 2 in Part A and 2 in Part C. There was a lack of correlation between measured GSK3358699 systemic concentrations and the NSVTs. Similar findings were not observed preclinically.	 Participant Selection / Monitoring / Stopping criteria: Specific eligibility criteria (see Section 6.2). Additional withdrawal criterion based on investigator and medical monitor judgement (see Section 8.1.6.). The protocol includes cardiac screening and monitoring (12 lead ECGs and telemetry) of participants at each dose level

2017N332348_05

CONFIDENTIAL

Potential Risk of Clinical Significance	Summary of Data / Rationale for Risk	Mitigation Strategy
		investigated. • Randomisation ratio in Part C has been changed to 1:1
		(GSK3358699:placebo)
		Relevant cardiovascular safety data from the current and any previous cohort will be considered as part of dose escalation decisions.

Potential Risk of Clinical Significance	Summary of Data / Rationale for Risk	Mitigation Strategy
Haemodynamic	 An increase in heart rate (increased by up to 46 beats per minute (bpm)) was observed after 13 doses of a non-tolerated 30 mg/kg/day dose in a single cynomolgus monkey with a 16 fold margin to the NOEL (free Cmax). No abnormalities were observed histologically in the hearts of rats or monkeys given GSK3358699 for up to 6 weeks. 	 Dose Selection: Doses administered as part of this study will not intentionally exceed the GSK3358699 AUC of 255 ng/ml.h, C_{max} 42 ng/ml which are the predicted AUC and C_{max} at 45 mg QD. Participant Monitoring: The protocol includes cardiac monitoring (vital signs, 12 lead ECGs and telemetry) of participants at each dose level investigated. Relevant cardiovascular safety data from the current and any previous cohort will be considered as part of dose escalation decisions.
Drug-Drug Interactions (DDIs)	GSK3358699 is a weak metabolism dependent inhibitor of Cytochrome P450 3A4 (CYP3A4) hence there is a risk of inhibiting CYP3A4 substrate con-meds resulting in clinically relevant DDIs.	 Study Design: GSK3358699 will not be administered with any other drug or known CYP3A4 substrate as part of this FTIH protocol. Human PK data generated as part of this study will be used with in vitro data to inform the DDI risk associated with GSK3358699 and future clinical mitigation strategies.

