5.2. Number of Participants

The number of healthy male participants and the required number of evaluable participants are outlined in Table 1.

Part	Participants per cohort	Evaluable participant number per cohort	Evaluable participant definition
A (Cohorts 1-2)	9 (6:3 GSK3358699 : Placebo)	6	Complete both screening and all their planned treatment Periods.
B (Cohort 3)	6 (all receive GSK3358699)	5	Complete both screening and both treatment Periods.
C (Cohort 4)	14 (10:4 GSK3358699 : Placebo)	9	Complete both screening and the 14 day treatment Period and subsequent 48 h assessment Period.
C (Cohorts 5-7)	18 (9:9 GSK3358699 : Placebo)	12	Complete both screening and the 14 day treatment Period and subsequent 48 h assessment Period
C (Cohort 8)	20 (10:10 GSK3358699 : Placebo)	14	Complete both screening and the 14 day treatment Period and subsequent 48 h assessment Period.

Table 1 Number of Participants

2017N332348_05

CONFIDENTIAL

Participants who are randomized into a particular part of the study can be enrolled in another part of the study, as well as be enrolled in a later cohort of the same part of the study in Part C, if they still fulfil all eligibility criteria (which means that participants having received LPS challenge in Part A will not be eligible to participate in another part of the study).

Additional participants/cohorts may be enrolled in Part A or Part C to allow for evaluation of additional dose levels or alternative regimens, including for challenges, as detailed in Section 7.2. No more than 9 additional participants will be included as part of a new cohort in Part A and no more than 20 additional participants will be allowed as part of a new cohort in Part C (ie in addition to Cohort 4-8 participants).

If participants prematurely discontinue the study during Part A, additional replacement participants may be recruited and assigned to the same treatment sequence, starting from the next planned dosing Period following the premature discontinuation, at the discretion of the Sponsor in consultation with the investigator.

If a participant chooses to participate in, or is eligible for, the dose escalation treatment Periods only in Part A as described in Section 5.1.1.1, a new participant will be recruited for the challenge treatment period (treatment Period 4) only and will be regarded as a replacement subject, assigned to the same treatment sequence. This will occur at the discretion of the Sponsor in consultation with the investigator.

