8.1.6. Individual Safety Stopping Criteria

• If a participant experiences a serious or severe clinically significant AE that in the clinical judgement of the Investigator, after consultation with the medical monitor, is possibly, probably or definitely related to investigational product, then the participant should be withdrawn from the study.

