8.1.10. Rechallenge

8.1.10.1. Study Treatment Restart or Rechallenge

Study treatment restart or rechallenge after any stopping criteria are met by any participant in this study is not allowed for that individual.

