9.4.5. Electrocardiograms

- Triplicate 12-lead ECGs will be obtained in the study at the time points detailed in the SoA and at other times in the study if clinically indicated (Section 2.3; single ECGs at all other time points) using an ECG machine that automatically calculates the heart rate and measures PR, QRS, QT, and QTcF intervals. Refer to Section 8.1.2 for QTc withdrawal criteria and additional QTc readings that may be necessary.
- At each time point at which triplicate ECG are required, 3 individual ECG tracings should be obtained as closely as possible in succession, but no more than 4 minutes apart. The full set of triplicates should be completed in less than 8 minutes.
- Holter monitoring will be performed at screening only. This 24-hour Holter will be performed to eliminate participants with non-clinically overt cardiac arrhythmias or other exclusionary criteria.

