9.8.2. Biomarkers in blisters

Biomarkers in blisters will be collected by piercing the blister with a needle and aspirating the blister contents with a pipette into a polypropylene micro-centrifuge tube. Cellular and soluble contents will be separated. The volume of the blister sample will be calculated and recorded in the eCRF. **[E3]**. The baseline blister samples collected will be repeated if > 4 months elapses between the baseline blister and the challenge treatment Period (eg if a reserve in the study is not dosed and is subsequently rescreened for a later cohort).

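### Exclusion #8, the Holter waiver and the NSVT withdrawal cross-reference do not fit together: NSVT seen on study is left to judgement, and a rescreened man's Holter has no expiry

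*Protocol*

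**What the plan says.** Protocol section 3.3.1 records the signal behind Amendment 4: "Four cases of asymptomatic, non-serious, non-severe and self-limiting NSVT were observed in this study (207546); 2 in Part A and 2 in Part C". It lists eligibility criteria and a withdrawal criterion in section 8.1.6 among the mitigations.

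The Amendment 4 summary of changes shows exclusion #8 as new: "Non-sustained ventricular tachycardia (NSVT) defined as ventricular triplet or longer), or more than 30 Ventricular Premature Depolarisation (VPD)/hour on screening Holter". The same amendment added to section 5.2 that a participant may "be enrolled in a later cohort of the same part of the study in Part C, if they still fulfil all eligibility criteria".

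On the Holter, section 9.4.5 states: "Holter monitoring will be performed at screening only". The general schedules (2.1 to 2.4) each carry the note "If a participant is rescreened the Holter will not need to be repeated", with no limit on the age of the recording. Section 5.1 places the screening visit within 35 days of first dose, or 45 days for Cohort 8. Section 6.4 speaks of rescreening for screen failures and for reserves who were not needed.

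One other baseline measure does expire. Section 9.8.2 says "The baseline blister samples collected will be repeated if > 4 months elapses between the baseline blister and the challenge treatment Period", and gives as its example an undosed reserve who is rescreened for a later cohort.

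On withdrawal, section 8.1.6 begins "If a participant experiences a serious or severe clinically significant AE that in the clinical judgement of the Investigator" and adds that the event must be judged at least possibly related. Section 8.1.10.1 says: "Study treatment restart or rechallenge after any stopping criteria are met by any participant in this study is not allowed for that individual".

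**The concern.** The rhythm exclusion is one of the stated mitigations for the only safety signal to emerge from this study's own clinical data. Amendment 4 tightened entry on rhythm and widened re-entry, but the two changes were not joined up.

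Two things are at stake. The first is participant safety: the protocol gives no explicit rule for a man who has already shown NSVT on study telemetry, and it lets #8 be satisfied by a recording of any age in a man who is rescreened. The second is attribution. The 1:1 ratio in Part C is itself listed as NSVT mitigation, because it gives a balanced comparison with placebo. Cohorts 5 to 7 have nine men per arm, so one man with known NSVT would be 1/9 = 11% of an arm. Randomisation balances such men in expectation, but that is little protection in a single cohort of this size.

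**Working it through.** The plan states no validity period for the Holter, so there is no figure to reproduce. The check compares passages, with some calendar arithmetic.

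**1. A man with asymptomatic, self-limiting NSVT on study telemetry who seeks a later Part C cohort**

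| Provision | What it needs | Does it settle the case? |
|---|---|---|
| Exclusion #8 | NSVT, or a VPD rate above 30 per hour, with the screening Holter named at the end | Unclear. A bracket closes that never opened. If the Holter phrase governs both limbs, telemetry NSVT does not count. If it governs only the VPD count, NSVT from any source excludes. |
| Exclusion #4 | A ventricular arrhythmia judged clinically significant | By judgement |
| Exclusion #7 | A clinically relevant abnormality on the screening ECG | By judgement, and only if the ECG shows it |
| Exclusion #9 | Investigator's opinion | By judgement |
| Inclusion #2 | Overtly healthy on medical evaluation, cardiac monitoring included | By judgement |
| 8.1.10.1 | A stopping criterion already met | Only if one was met (step 3) |

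On the narrow reading of #8, no explicit rule decides the case. Section 9.4.5 says the Holter is there to find arrhythmias that are not clinically overt, which is the kind of finding that #4 and #7 are least suited to catch.

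**2. Age of the Holter**

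For an undosed reserve no inference is needed. Section 6.4 allows him to be rescreened for a later cohort, and section 9.8.2 foresees more than 4 months between his baseline blister and the challenge period. The schedules place the screening Holter before the Day -10 blister visit, so his Holter is at least as old as the blister.

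- 4 months × 30.4375 days = 121.75, about 122 days
- 121.75 / 35 = 3.5 times the 35-day window
- 121.75 / 45 = 2.7 times the 45-day window of Cohort 8

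At that point the exploratory blister baseline is renewed and the Holter is not.

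For a previously dosed man, the figures hold only if the waiver reaches him. Section 5.1.1.3 gives Part A a duration of about 19 weeks (three periods) or 23 weeks (four periods), including screening and follow-up. Assume the Holter was done at the start of screening and there was no further wait before Part C:

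- 19 × 7 = 133 days; 133 / 35 = 3.8 windows
- 23 × 7 = 161 days; 161 / 35 = 4.6 windows

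**3. Section 3.3.1 against section 8.1.6**

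Section 3.3.1 points to 8.1.6 as the additional withdrawal criterion for NSVT. Section 8.1.6 requires a serious or severe event. Section 3.3.1 describes all four NSVTs as neither, so 0 of 4 meet the criterion on its wording. The bar in 8.1.10.1 depends on a stopping criterion having been met, so these events do not trigger it through 8.1.6.

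**4. Was the re-entry route used?**

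SAP section 5.4 and the footnote to Table 1.1 list three men: Cohort 1 to 4, Cohort 2 to 5 and Cohort 4 to 5. Cohort 4 ended on 14 November 2018 (SAP 13.6.1), before Amendment 4 of 11 December 2018. Only the two entries into Cohort 5 therefore fall under the amended criteria.

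**The case against.** The strongest reply is that the waiver was never meant for dosed men. Section 6.4 uses rescreening for screen failures and unused reserves, and the blister example concerns an undosed reserve. Section 5.2 describes re-entry as enrolment. The SAP gives re-enrolled men a separate subject number for each cohort and treats them as distinct participants. Every participant has a screening visit within 35 or 45 days of first dose, and the Holter is marked at that visit. On this reading a re-enrolled man has a new Holter, and the waiver merely spares a recent screen failure a second 24-hour recording. This is a fair reading and may be the intended one. It stands as a reason not to assert that dosed men re-enter on old recordings. It does not settle the matter, because the protocol nowhere says which reading applies, and it leaves the case of the reserve untouched.

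Other objections also stand in part. A reader might infer that a man with NSVT on study can simply re-enter. The documents do not support that: inclusion #2 and exclusions #4, #7 and #9 must all be satisfied, section 8.2 allows withdrawal for safety at any time, and #8 has a reading that excludes him. A reader might also see the waiver as contradicting the screening window. It is better described as an exception for one test, written without a limit.

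On 8.1.6, it can be said that section 3.3.1 promises only a criterion resting on investigator and medical monitor judgement, which 8.1.6 provides. That is true of who decides. It does not remove the threshold, which events like those described do not reach.

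**Conclusion.** The concern holds in this form: the provisions for NSVT leave one case without an explicit rule, one recording without an expiry, and one cross-reference pointing to a criterion that the observed events would not meet.

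For an undosed reserve the protocol's own example implies a Holter more than 4 months old, at least 3.5 times the 35-day window or 2.7 times the 45-day window. This rests on the Holter preceding the baseline blister. The 133 to 161 days for a previously dosed man depend on the waiver reaching him, which the documents do not state.

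Three re-enrolments show that the route was used. They do not show harm: no document says that any of these men had NSVT or entered on an old Holter. The effect on attribution is not quantified. The point merits correction because the signal is the reason for the amendment and the edits are short, but judgement-based safeguards remain, so it is not a defect that must be fixed before anything else can proceed.

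**What to change.** Make three wording changes.

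1. In section 6.2, reword exclusion #8, including its bracket, so that it states unambiguously which recordings count for NSVT and for the VPD rate, and how ECG, Holter or telemetry recordings already made in this study are treated.
2. In the Holter notes of sections 2.1 to 2.4, and in sections 5.2 and 6.4, state whether a previously dosed man who re-enrols counts as rescreened and so falls under the waiver. Bring the Holter's validity into line with the protocol's own screening window.
3. Reconcile section 3.3.1 with section 8.1.6, so that the criterion cited for NSVT and the events described as NSVT correspond.

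The clinical thresholds and the withdrawal rule are for the sponsor to decide; this review asks only that the passages agree.

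The cost is a few sentences, a few repeats of a 24-hour Holter that is already scheduled for new entrants, and possibly one or two fewer eligible volunteers. The first and third changes need no new procedure.
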